15.3 Deviations

A protocol deviation is defined as any instance during the conduct of the study in which the investigator or other site personnel changed or failed to adhere to the study design or procedures specified by the protocol. Investigative sites are expected to comply with the study protocol except where necessary to protect the life or physical well-being of a subject in cases of medical emergency,

Throughout the conduct of the study, data will be reviewed by Sponsor for the presence of deviations. Study personnel will report any deviation from the study protocol or regulation upon occurrence. Sponsor monitors will also review data and conduct for any deviations during on-site visits per the monitoring plan.

15.4 Data storage/archives

The investigators must maintain adequate and accurate records to document the conduct of the clinical study and to substantiate the clinical study data. These records include regulatory documents as required by applicable regulations, and the subjects' source documents, clinical trial progress records, laboratory reports, electronic case report forms, signed informed consent forms, device accountability records, correspondence with the EC and clinical trial monitor or sponsor, adverse event reports, and information regarding subject discontinuation or completion of the clinical trial/investigation.

Regulatory documents are those documents that individually and collectively permit evaluation of study compliance with applicable regulations and evaluation of the quality of the data produced.

These documents will be filed in an Investigator Site File provided by the Sponsor or designee. This file shall be used to facilitate and ensure filing of all relevant regulatory documents during and after the study. The investigator will be responsible for keeping the Investigator Site File updated and ensuring that all required documents are filed. The file will be inspected during monitoring visits.

SAFE-2023 Colovac 2 Study Clinical Investigation Plan

The investigator shall arrange for the retention of all study documents and records, including subject records, eCRFs, device inventory/accountability log, signed informed consent forms and the patient identification list for at least 15 years, or as per local regulatory requirements, after completion or discontinuation of the study.

16.0 Regulatory Responsibilities

16.1 Investigator Responsibilities

The Principal Investigator is responsible for ensuring the investigation is conducted according to the CIP and all signed agreements by the investigative team. The Investigator is not allowed to deviate from the CIP. This section describes these responsibilities at his/her site. Also, the Principal Investigator and participating sites must complete and sign the Clinical Trials Agreement contract, and the Principal Investigator must complete and sign the Investigator Agreement prior to enrollment of the first subject.

The investigator must submit the study protocol to his/her Ethics Committee and obtain their written approval before being allowed to consent a subject in the study. The investigator is also responsible for fulfilling any conditions of approval imposed by the Ethics Committee, such as regular reporting, study timing, etc.

Part of the Ethics Committee approval must include approval of an Informed Consent text specific to the trial. The investigator or staff must administer this approved Informed Consent text to each prospective study patient, and obtain the patient's signature on the text, prior to enrollment in the study.

Informed Consent

Subject participation in this clinical trial is voluntary. Informed Consent is required from each subject. The Investigator is responsible for ensuring that Informed Consent is obtained prior to the use of any procedures, testing or data collection being done specifically for the trial.

The ICF must be in a language understandable to the subject and privacy language shall be included in the body of the form or as a separate form as applicable. Approval from the EC is necessary before the ICF can be used.

The process of obtaining Informed Consent shall at a minimum include the following steps, as well as any other steps required by applicable laws, rules, regulations, and guidelines:

- Be conducted by the Principal Investigator or designee authorized to conduct the process
- Include a description of all aspects of the clinical trial that are relevant to the subject's decision to participate throughout the clinical trial
- Avoid any coercion of or undue influence of subjects to participate
- Not waive or appear to waive subject's legal rights

SAFE-2023 Colovac 2 Study Clinical Investigation Plan

- Use native language that is non-technical and understandable to the subject or his/her legal representative
- Provide ample time for the subject to consider participation and ask questions if necessary
- Ensure important new information is provided to new and existing subjects throughout the clinical trial

The ICF shall always be signed and personally dated by the subject and by the investigator and/or an authorized designee responsible for conducting the informed consent process.

If the subject is unable to read or write, an impartial witness should be present for the entire informed consent process (which includes reading and explaining all written information) and should personally date and sign the informed consent form after the oral consent of the subject is obtained.

The original signed ICF will be retained by the site and a copy of the signed and dated document, and any other written information must be given to the person signing the form. Subjects may withdraw consent at any time throughout the course of the trial.

The consent process, including the name of the individual obtaining consent, will be thoroughly documented in the subject's research record. Any alteration to the standard consent process (e.g., use of a translator, consent document presented orally, etc.) and the justification for such alteration will likewise be documented.

If new information becomes available that can significantly affect a subject's future health and medical care, that information shall be provided to the affected subject(s) in written form via a revised ICF or, in some situations, enrolled subjects may be requested to sign and date an addendum to the ICF. In addition to new significant information during the course of a trial, other situations may necessitate revision of the ICF, such as if there are amendments to the applicable laws, protocol, a change in Principal Investigator, administrative changes, or following annual review by the IRB/IEC. The new version of the ICF must be approved by the IRB/IEC, who will also determine the subject population to be re-consented.

16.1.1 Records

The Study Team will be comprised of the Principal Investigator (PI), investigators, the study coordinator(s), members of SafeHeal, contractors designated by SafeHeal, or any other staff as prescribed by the PI. The members of the study Team will be documented on a delegation log or study staff log prior to enrollment of the first subject. Amendments after enrollment of the first subject may be made and will be documented by the PI.

The Principal Investigator is responsible for maintaining the following (the responsibilities may be delegated by the Principal Investigator to the Study Coordinator):

- Accurate, complete, and current records relating to the conduct of the study. The data for some of these reports may be available in electronic form but must be made available for monitoring by the Sponsor or monitor.

SAFE-2023 Colovac 2 Study Clinical Investigation Plan

- All correspondence with study investigators, an IRB/Ethics Committee, the sponsor, a monitor, or competent authorities, notified bodies or the FDA, including required reports.
- Records of receipt, use, or disposal of the study device, including receipt dates, serial and lot numbers, names of all persons who received or used the device, why and how many devices were returned to the sponsor or otherwise disposed of.
- Records of each subject's case history, including study-required Case Report Forms, evidence of informed consent, all relevant observations of adverse device effects, the condition of each subject upon entering and during the course of the investigation, relevant medical history, the results of all diagnostic testing, and the date of each study treatment.

16.1.2 Reports

The principal investigator shall report all adverse events and device deficiencies in the appropriate sections of the e-CRF and provide where requested by the sponsor, the necessary clinical or technical information that may contribute to clarifying the circumstances.

The principal investigator shall report:

- a) any serious adverse event (SAE) that has a causal relationship with the investigational device, or the investigation procedure or where such causal relationship is reasonably possible.
- b) any device deficiency (DD) that might have led to a serious adverse event if appropriate action had not been taken, intervention had not occurred, or circumstances had been less fortunate.
- c) any new findings in relation to any event referred to in points a) and b).

to the sponsor immediately, but not later than 3 calendar days after investigation site study personnel's awareness of the event, using the appropriate page of the e-CRF. In case of any eCRF system failure, a paper CRF page may be completed and sent to the sponsor following the same time requirements.

Reporting of adverse events starts from the time point the subject is enrolled in the clinical investigation (i.e., signed informed consent). This means that any adverse events related to or reported during the screening assessments are to be reported.

The principal investigator shall document all adverse events and device deficiencies in the e-CRF that occur any time after informed consent is obtained until 7 days (for non-serious AEs) or 30 days (for SAEs) after the last day of trial participation.

Every SAE will be followed-up until the event is resolved, resolved with sequelae, or until study closure, whichever occurs first.

When required by national or local regulations, the principal investigator shall also notify the EC of all reportable events according to national regulations within the by regulations required timelines and may also be requested by the EC to provide annual reports.

16.1.3 Information provided by the clinical investigation site

SAFE-2023 Colovac 2 Study Clinical Investigation Plan

The principal investigator will provide the following information, at a minimum, for each adverse event (AE) or Adverse Device Effect (ADE):

- Date of the AE or ADE onset.
- Date Principal Investigator (or authorized designee) became aware of AE or ADE
- Description of AE or ADE and circumstances (detailed description of course of event)
- Treatment
- Resolution
- Assessment of:
 1. Seriousness
 2. Severity of the event
 - f. Mild: asymptomatic or mild symptoms; clinical or diagnostic observations only; intervention not indicated.
 - g. Moderate: minimal, local or noninvasive intervention indicated; limiting
 - h. Severe: medically significant but not immediately life-threatening; hospitalization or prolongation of hospitalization indicated; disabling
 - i. Life-threatening: urgent intervention indicated, disabling
 - ii. Fatal: death related to AE
 3. Relationship of the event to the investigational device (Not related, possible, probable, or causal [definite] relationship).
 4. Relationship of the event to the index procedure (Not related, possible, probable, or causal [definite] relationship)
 5. If not related to study device or study procedure, causality with
 - a. disease under study
 - b. lack of performance of the investigational device or comparator/worsening of treated condition
 - c. medical history (current/past)
 - d. concomitant or previous medication
 - e. technical issue of the other products used
 - f. other (specify)

In addition, the severity of the event will be assessed using a Clavien-Dindo Classification as discussed in section 14.2.

Table 6 displays a list of the reports that are the Principal Investigator's responsibility to generate. The table also shows to whom the report is to be sent, and with what frequency or time constraints. While some of these reports will be developed by or with the assistance of the Sponsor, the final responsibility for them rests with the PI. The responsibilities may be delegated by the Principal Investigator to the Study Coordinator.

Table 6: Reports Required from Clinical Investigators

Type of Report	Prepared by Investigator for:	Time Constraints of Notification
Patient death	Sponsor	Immediately (but not later than 3 calendar days)

SAFE-2023 Colovac 2 Study Clinical Investigation Plan

Type of Report	Prepared by Investigator for:	Time Constraints of Notification
Unanticipated adverse event	Sponsor	Immediately (but not later than 3 calendar days)
Report of patient enrollment	Sponsor	Within 5 working days
Serious adverse event that has a causal relationship with the investigational device, or the investigation procedure or where such causal relationship is reasonably possible	Sponsor	Immediately (but not later than 3 calendar days)
Device deficiency that might have led to a serious adverse event	Sponsor	Immediately (but not later than 3 calendar days)
Patient withdrawal	Sponsor	Within 5 working days
Withdrawal of Ethics Committee approval	Sponsor	Within 5 working days
Deviations from investigational plan	Sponsor	Within 5 working days
Informed consent not obtained	Sponsor	Within 5 working days
Final summary report	Sponsor	Within 3 months

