6.2 Anticipated Risks

All patients will be exposed to the potential risks associated with all medical procedures (including death). Potential adverse events include the following:

1. The general complications of any colorectal surgery.
 - a) Pelvic complications
 - i. Anastomotic bleeding
 - ii. Anastomotic stricture
 - iii. Anastomotic fistula
 - iv. Anastomotic leakage
 - v. Anastomosis dehiscence
 - vi. Pelvic abscess, collection
 - vii. Colonic ischemia
 - viii. Peritonitis
 - b) Ileus
 - c) Small bowel obstruction
 - d) Incisional hernia
 - e) Bleeding
 - f) Organ injury (e.g., bladder, bowel, ureter)
 - g) Nerve tissue injury
 - h) Surgical Site Infection
 - i) Prolapse
 - j) Acute renal failure
 - k) Sepsis
 - l) AEs associated with potential stoma placement/stoma reversal
 - m) Death
2. Adverse events that may probably be caused by or associated with the use of the Colovac 2 Device (during and after implant period) include:
 - a) Complications from device malfunction that lead to early removal of device and stoma conversion (e.g., migration, stent collapse) such as:
 - i. Pelvic complications (abscess, collection)
 - ii. Anastomosis complications (leakage, fistula, dehiscence)
 - iii. Peritonitis
 - iv. Sepsis
 - v. Colon perforation, obturation or occlusion
 - vi. AEs associated with stoma conversion procedure
 - b) Ileus
 - c) Small bowel obstruction
 - d) Colonic ischemia
 - e) Colonic stenosis
 - f) Colon wall damage (e.g., inflammation, hyperplasia, fibrosis, edema, erosion, ulceration)
 - g) Abdominal/Anal pain
 - h) Temporary feces and gas incontinence

SAFE-2023 Colovac 2 Study Clinical Investigation Plan

-
- i) Diarrhea or constipation
 - j) Inflammation of skin around the anus
 - k) Prolapse
 - l) Complication associated with an attempt to reposition the Colovac 2 Device (although Warnings instruct not to re position the Colovac Device)
 - m) Complication associated with having to remove the Colovac 2 Device surgically – if endoscopic retrieval is impossible
 - n) Adjacent organ injury due to a broken stent wire poking through the colon
 - o) Additional complications reported for other colorectal stents:
 - i. Tenesmus
 - ii. Fecal impaction
 - iii. Bacteremia/fevers
 - iv. Foreign body sensation
 - v. Intestinal colic (pain not related to operative site)
 - vi. Bleeding/blood from anus
 - vii. Nausea
 - viii. Inability to eat
 - ix. Cramping
3. Medication side effects, especially anesthesia reactions, including:

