9.4 Primary Objective

SAFE-2023 Colovac 2 Study Clinical Investigation Plan

The primary study objective is to evaluate the clinically significant (CS) migration rate of the Colovac 2 device during its 10-day implantation period.

9.5 Primary Performance Endpoint at Day 10

The primary performance endpoint is the clinically significant migration rate of the Colovac 2 device during its 10-day implantation period.

Clinically significant migration is defined as movement of device that allows fecal contents to reach the anastomosis site evidenced by:

- Migration of entire stent to or below the Sacral Promontory as indicated by fluctuation in the length of the sheath that extends out of the anus and confirmed by radiographic displacement, with or without subject symptoms or clinical findings suggestive of anastomotic leak (pain, fever, elevated CRP, elevated WBC); or
- Expulsion of the device.

9.6 Secondary Objectives:

The secondary objectives of this study are to assess the:

- Preliminary safety and performance of the Colovac 2 System
- Ease of use of the Colovac 2 Colorectal Anastomosis Protection Device
- Ease of use of the Colovac 2 Introducer and Implant and Vacuum Management Device

9.7 Other Performance Endpoints at Day 10

The other performance endpoints are:

- Ostomy avoidance rate
- Cleanliness of colon immediately prior to device retrieval
- Staff Ease of Use of Device
- Subject Tolerance and Ease of Use of Device

9.8 Safety Endpoints at Day 10

The safety endpoints are:

- Mucosal appearance at anchoring site after device removal
- Device related complications
- All complications

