14.0 Safety

14.1 Device Deficiency

According to ISO14155:2020, the definition of a device deficiency is:

Any inadequacy of a medical device with respect to its identity, quality, durability, reliability, usability, safety, or performance. Device deficiencies include malfunctions, use errors, and

SAFE-2023 Colovac 2 Study Clinical Investigation Plan

inadequacy in the information supplied by the manufacturer including labeling. This definition includes device deficiencies related to the investigational medical device or the comparator.

All investigational device deficiencies will be documented in the eCRF. Devices that undergo such deficiency will be returned to the device legal manufacturer (SafeHeal) for analysis in the biohazard boxes provided with relevant CRFs for deficiency.

Recall can be triggered by Legal Manufacturer based on complaint analysis or by FDA or National Competent Authorities decision. According to sponsor internal procedure, immediate identification of devices and location are given by a specific tracker managed by the sponsor. Recall actions and recording follows internal sponsor procedure.

The above-mentioned devices must be returned to SafeHeal after appropriate decontamination per hospital guidelines.

The Sponsor and the Investigators will use the following definition to determine if a device deficiency could have led to a serious adverse event.

Device deficiencies that might have led to a serious adverse event

- a) if appropriate action had not been taken,
- b) intervention had not occurred, or
- c) circumstances had been less fortunate,

shall be reported under the same conditions as a serious adverse event. Note: FDA recognizes an earlier version of this global consensus standard (ISO14155:2011).²

Malfunction

According to ISO 14155:2020, the definition of a malfunction is:

Failure of an investigational medical device to perform in accordance with its intended purpose when used in accordance with the instructions for use or Clinical Investigation Plan or Investigator Brochure.

Use Error

According to ISO 14155:2020, the definition of a use error is:

User action or lack of user action while using the medical device that leads to a different result than that intended by the manufacturer or expected by the user

Note 1: Use error includes the inability of the user to complete a task.

Note 2: Use errors can result from a mismatch between the characteristics of the user, user interface, task or use environment.

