14.2 Adverse Events

All Adverse Events will be recorded on the AE eCRF.

Definitions

Adverse Events (AE) per ISO 14155:2020

The definition of an adverse event is:

Any untoward medical occurrence, unintended disease or injury or untoward clinical signs (including an abnormal laboratory finding) in subjects, users, or other persons, whether or not related to the investigational medical device and whether anticipated or unanticipated.

Note 1: This definition includes events related to the investigational medical device or the comparator.

Note 2: This definition includes events related to the procedures involved

Note 3: For users or other persons this definition is restricted to events related to the use of the investigational medical devices or comparators.

Serious Adverse Events (SAE) per ISO 14155:2020

The definition of a Serious Adverse Event is:

Any adverse event that led to any of the following:

- a) death,
- b) serious deterioration in the health of the subject, users or other persons as defined by one or more of the following:
 - 1) a life-threatening illness or injury,
 - 2) a permanent impairment of a body structure or a body function, including chronic disease or
 - 3) in-patient or prolonged hospitalization, or
 - 4) medical or surgical intervention to prevent life threatening illness or injury, or permanent impairment to a body structure or a body function.
- c) fetal distress, fetal death or a congenital abnormality, or birth defect including physical or mental impairment

Note: Planned hospitalization for a preexisting condition, or a procedure required by the CIP without serious deterioration in health is not considered as a serious adverse event.

SAFE-2023 Colovac 2 Study Clinical Investigation Plan

Unanticipated Adverse Device Effect (UADE) per 21CFR 812.3(s)

Any serious adverse effect on health or safety or any life-threatening problem or death caused by, or associated with, a device, if that effect, problem, or death was not previously identified in nature, severity, or degree of incidence in the investigational plan or application (including supplementary plan or application), or any other unanticipated serious problem associated with a device that relates to the rights, safety, or welfare of subjects.

Adverse Device Effect (ADE) per ISO 14155:2020

An adverse event related to the use of an investigational medical device.

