Note 1: This definition includes adverse events resulting from insufficient or inadequate instructions for use, deployment, implantation, installation, or operation, or any malfunction of the investigational medical device.

Note 2: This definition includes any event resulting from use error or from intentional misuse of the investigational medical device.

Note 3: This includes 'comparator' if the comparator is a medical device.

Serious Adverse Device Effect (SADE) per ISO 14155:2020

Adverse device effect that has resulted in any of the consequences characteristic of a serious adverse event.

Unanticipated Serious Adverse Device Effect (USADE) per ISO 14155:2020

A serious adverse device effect which by its nature, incidence, severity, or outcome has not been identified in the current risk assessment.

Note 1: Anticipated serious adverse device effect (ASADE) is an effect which by its nature, incidence, or severity or outcome has been identified in the risk assessment.

Serious Health Threat per ISO 14155:2020

Signal from any adverse event or device deficiency that indicates an imminent risk of death or a serious deterioration in the health in subjects, users, or other persons, and that requires prompt remedial action for other subjects, users or other persons.

Note 1: This would include events that are of significant and unexpected nature such that they become alarming as a potential serious health hazard or possibility of multiple deaths occurring at short intervals.

AE Reporting

All the adverse events identified by the physician or the patient during the study must be reported as soon as possible on the AE eCRF, regardless of classification, seriousness, severity, outcome, or

**SAFE-2023 Colovac 2 Study
Clinical Investigation Plan**

causality. Additional documentation may be requested by the Sponsor including, but not limited to, a written subject narrative detailing the clinical course of the AE.

All AEs must be documented in the in the Adverse Event eCRF including:

- Description of the event
- Date of onset
- Relationship to the LAR procedure (index surgery), investigational Colovac device (including implantation and removal procedures), SmartVac System, Canisters with tubing sets, and stoma (including creation and reversal procedures).

For the purpose of harmonizing reports, each AE will be classified according to four different levels of relationship (causality):

1. Not related
2. Possible
3. Probable
4. Causal (Definite) relationship

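### Section 16.1.3 offers lack of device performance as a cause of events rated not device-related, contradicting 14.1, 14.2 and 6.2; non-serious events so coded can miss committee review and the device-related endpoint

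*Combined protocol and SAP*

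**What the plan says.** Section 16.1.3 lists what the site must assess for each adverse event. Item 3 asks for "Relationship of the event to the investigational device (Not related, possible, probable, or causal [definite] relationship", and item 4 asks the same for the index procedure. Item 5 opens only after negative answers: "If not related to study device or study procedure, causality with". Its option b is "lack of performance of the investigational device or comparator/worsening of treated condition".

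Other sections classify device failure differently:

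- **Section 14.1** defines a malfunction as "Failure of an investigational medical device to perform in accordance with its intended purpose", given use according to the instructions, the plan or the brochure.
- **Section 14.2** defines an adverse device effect (ADE) as "An adverse event related to the use of an investigational medical device". Note 1 extends this to events resulting from inadequate instructions "or any malfunction of the investigational medical device". Note 2 adds events from use error or intentional misuse.
- **Section 6.2** lists, among events the device may cause, "Complications from device malfunction that lead to early removal of device and stoma conversion", with migration and stent collapse as examples.

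Section 9.8 names "Device related complications" as one of three Day 10 safety endpoints. It gives no causality cut-off and does not say whose rating counts.

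**The concern.** The protocol gives two answers for the same event. If a complication arose because the device did not do its job, 14.1 and 14.2 make it an ADE. Item 5b lets the site name that same cause while keeping the rating at not related. The form could even encourage this: among the grounds for a not-related rating, 14.2 includes attribution to another cause, and 5b presents device failure as if it were one.

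This matters because anchoring failure is what the study was set up to examine. Section 4.3 reports that SAFE-2 enrollment closed after unpredictable vacuum performance was found to be the root cause of migration. Migration of any kind occurred in 4 of 15 SAFE-2019 subjects in the APP cohort and in 6 of the last 12 SAFE-2 subjects. Minor complications after partial migration or vacuum loss are therefore foreseeable. If they are filed as unrelated, the device-related complication rate is too low.

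**Working it through.** The plan states no expected device-related complication rate, so there is no figure to reproduce. The check traces what happens to an event, then gives its scale.

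**Step 1: is there a contradiction?** Take an event that the site attributes to the device not performing.

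- If the device was used as instructed, failure to perform as intended is a malfunction (14.1). The event is an ADE under 14.2, Note 1.
- If it was not used as instructed and a use error or misuse led to the event, it is an ADE under 14.2, Note 2.

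In both cases 14.2 makes it device-related, whereas item 5b is available only to events rated unrelated. The sections cannot both be followed.

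**Step 2: which miscoded events would be corrected?** Section 14.2 says the CEC adjudicates relatedness and that its decision is the one analysed. Section 14.3 lists what the CEC assesses: serious adverse events, ADEs, anastomotic leaks, and index-surgery or ostomy-related events of Clavien-Dindo grade III-V (or grade II with readmission).

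| Event, coded not related with cause 5b | Reaches the CEC under 14.3? | Rating used in analysis |
|---|---|---|
| Serious | Yes, whatever the site code | CEC |
| Anastomotic leak, serious or not | Yes, whatever the site code | CEC |
| Non-serious, not a leak, but index-surgery or ostomy-related at the listed grades | Yes | CEC |
| Any other non-serious, non-leak event | Not listed: by its code it is not an ADE | Site code can stand |

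The last row is the gap. Section 6.2 suggests candidates: abdominal or anal pain, inflamed skin around the anus, temporary incontinence. The third row offers little rescue, because item 5 also presupposes no relation to the study procedure.

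**Step 3: which other outcomes are touched?** Clinically significant migration (9.5) is defined by stent position or expulsion, so causality coding does not enter it. The endpoint of all complications (9.8) counts the event whatever its cause. Only the device-related endpoint is exposed.

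**Step 4: scale.** Inputs: n = 50 (the maximum in section 9.0) and two-sided 95% intervals (13.0), computed here by the exact Clopper-Pearson method. The event counts are assumptions for illustration.

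- One subject missed: 1/50 = 2.0 percentage points.
- If 5 subjects truly had a device-related complication: 5/50 = 10.0% (95% CI 3.3 to 21.8).
- If two of those five are missed: 3/50 = 6.0% (95% CI 1.3 to 16.5).

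This assumes that the rate counts subjects and that a missed subject has no other event counted as device-related. With fewer than 50 subjects, each one weighs more.

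**The case against.** The strongest reply is that the form does not reclassify anything. Device relatedness is asked first, in item 3. Under 14.2 a weak link that cannot be ruled out is possible, and so is a case that cannot be assessed. A site that blames migration and still enters not related has misapplied 14.2. The sponsor also assesses relatedness, and the CEC has the final say. The CEC Charter and the separate SAP that section 13.0 relies on are not in the text reviewed, and either may close the gap. Most of this stands, and it limits the point to an inconsistency that permits error. It does not remove the conflict from the protocol that sites follow, and CEC review helps only for events that reach the CEC.

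Three stronger readings are tempting, and the documents do not support them:

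- **Complications of device failure in general leave the endpoint.** The serious ones and all leaks go to the CEC regardless of the site code. An abscess after migration, for example, would very probably be serious, and a perianastomotic collection may count as a grade A leak (Appendix 3).
- **Serious events bypass the sponsor.** The 16.1.2 report is limited to events with a causal or reasonably possible link, but 14.2 requires every serious event on the AE form within 3 days, with no relatedness condition.
- **The bias can be sized from earlier migration rates.** The documents do not say what share of migrations cause a complication, or how often sites would choose 5b. Using only the 3 of 12 from late SAFE-2 omits the earlier group, with none among 14. With SAFE-2019 (2 of 15), the total is (2 + 0 + 3)/(15 + 14 + 12) = 5/41 = 12.2%, and that is for an earlier device with a different vacuum source.

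**Conclusion.** The contradiction between 16.1.3 item 5b and sections 14.1, 14.2 and 6.2 is clear from the text and should be reconciled. Its consequence is narrow: non-serious, non-leak events coded not related with cause 5b can keep that code and be missed from the Day 10 device-related complications. Any bias from this route lowers the rate, by 2 percentage points per subject missed at n = 50. How many subjects would be missed cannot be estimated from the documents.

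The conclusion assumes that CEC case selection follows the list in 14.3 and that neither the Charter nor the SAP adds a rule for these events. The wording conflict is certain; the bias is only possible. The primary result is not threatened, but the change is worth making because the affected endpoint is one of three named safety endpoints.

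**What to change.** 1. In 16.1.3 item 5, remove lack of performance of the investigational device from the not-related branch. Keep worsening of the treated condition as its own option.
2. State in 14.2 and 16.1.3 that an event attributed to lack of performance of any Colovac 2 System component, including the vacuum device and its canisters and tubing, is handled as an ADE and sent to the CEC. The CEC decides final relatedness, so its judgment is not pre-empted.
3. Define the device-related complications endpoint in 9.8 and the SAP by CEC-adjudicated relatedness, naming the categories that count and whether subjects or events are counted.
4. Enrollment began on July 31, 2024 (section 9.2), so send any event already coded 5b to the CEC.

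The cost is one form edit, a few sentences of protocol and SAP text, and some additional CEC reviews in a study of at most 50 subjects. The device-related rate may come out slightly higher.
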